7.10 Safety Evaluation

An Adverse Event (AE) is any untoward medical occurrence, unintended disease or injury, or untoward clinical signs (including abnormal laboratory findings) in subjects, users or other persons, whether or not related to the investigational medical device.

This definition includes events related to the investigational medical device and the procedures involved. For users or other persons, this definition is restricted to events related to investigational medical devices.

Adverse Events may include but are not limited to pain, bleeding, nausea, vomiting, and headache.

AEs will be reported by frequencies and percentages of subjects by categories of AEs and by count of each AE. A listing will also be provided.

AEs will be collected and documented at baseline and 0 to 14 days follow-up. AEs will be presented globally and based on their occurrence periods: PRE-PROCEDURE, DURING PROCEDURE and POST-PROCEDURE. The MedDRA coding system will be used so as to report the AEs in the statistical tables.

Safety analysis will be run on the whole ITT population and on the FAS.

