9.1. Schedule of Events

9.1.1. Study Schematic

Subjects who meet the eligibility criteria will be considered for study participation. The schematic of the trial is presented in the table below.

Table 1: Study Schematic

	Screening / Baseline Day -30 to 0	Surgery (Day 0)	Post-Op Follow-Up Day 1 – Day 7 (Home)	Post-Op Follow-Up Day 10 (Home)	Post-Op Follow-Up Day 14 (+3 days)
Informed Consent Form ¹	X	x			x
Eligibility Criteria	x	x			
Urine pregnancy test (female Pts; US only) ²	x	x			
Demographic data	x				
Medical history	x				
Surgical history	x				
Medication history	x				
Concomitant medications		x	x	x	X
Type of admission		x			
Physical Examination		x			
Intra-operative bleeding volume		x			
Tonsil measurement		x			
Surgical technique		x			
Operation time		x			
Device ease of use		x			
Dissection assessment		x			
Alternate device used (if any)		x			
Post-operative bleeding			x	x	x
AE, SAE, ADE, USADE Assessment & Device Deficiencies ³		x	x	x	x
Readmission			x	x	x
QOL Home survey (EORTC QLQ – H&N35) • Ability to return to normal diet • Ability to return to normal activity			x	x	x
Pain via VAS scale (Appendix B)			x	x	x
Return to clinic follow-up visit					x
Return VAS and QoL questionnaire					x
Device accountability		x			
Protocol deviation collection	x	x			x

¹ No study procedures will be performed until informed consent form has been completed.
²Urine pregnancy test (US only): unless female subject is surgically sterile or postmenopausal for at least 2 years. Confirmed by PI judgment and subject signature and noted in medical history and eCRF.
³AEs/SAEs must be followed to resolution or 30 days post EOS, whichever is first.

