9.1.2. Screening / Baseline Visit

A screening/baseline visit will be performed within 30 days up to/on the day of the scheduled procedure. Subjects will be consented prior to enrollment in the study before any procedures specific to the study are undertaken. The purpose and all aspects of the study will be explained to the subject. Subjects who

agree to study participation must sign and personally date the sponsor and an IRB/EC-approved informed consent form prior to participating in any study activities.

Once informed consent has been signed and eligibility is confirmed, the subject's demographics and medical history will be assessed to include: age, gender and weight.

- Relevant medical history will be assessed based on clinical condition categorized by category codes specified in the electronic case report form (eCRF).
- Female subjects will be assessed for childbearing potential, and if they do have childbearing potential, they will undergo a urine pregnancy test (US only). If the test is positive, they will be withdrawn from the study. If the pregnancy test is negative, these subjects should practice contraceptive methods through the course of the study. Additional urine pregnancy test will be performed on the day of surgery (US only). In Europe female subjects of childbearing potential will be asked pregnancy status. Women who respond as pregnant will not be included.

The following assessments will be performed within 30 days prior to the scheduled surgical procedure and the results recorded on the appropriate subject eCRFs:

- Verification of preoperative eligibility criteria
- Verification of surgical candidacy
- Demographic data
- Medical history, including concomitant medications and comorbidities
- Surgical history
- Medication history
- Pregnancy test, if applicable (US only)
- Concomitant medication(s)

Note: All medications will be coded using the World Health Organization (WHO) drug coding dictionary.

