9.7. Assessment of Safety

Safety will be assessed by monitoring the occurrence of adverse events (AEs), serious adverse events (SAEs), death, adverse device effects (ADE), unanticipated serious adverse device effects (USADE), device deficiencies or the presence of focal infection. Assessments will take place during the procedure through post-operative day 14 and will be recorded in the eCRF.

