11.1. Definitions/Classifications

11.1.1. Adverse Event (AE)

In alignment with ISO 14155:2011 (Section 3.2), an Adverse Event is any untoward medical occurrence, unintended disease or injury, or untoward clinical signs (including abnormal laboratory findings) in subjects, users or other persons, whether or not related to the investigational medical device.

This definition includes events related to the investigational medical device and the procedures involved. For users or other persons, this definition is restricted to events related to investigational medical devices.

For study purposes, the following occurrences are considered to be expected observations and will not be considered reportable Adverse Events, as long as the event is not associated with significant sequelae, does not prolong hospitalization and responds to standard medical therapy:

- Postoperative transient nausea determined to be procedure and/or medication related.
- Postoperative transient emesis determined to be procedure and/or medication related.
- Postoperative inflammation determined to be a part of every healing process.
- Postoperative headaches determined to be procedure and/or medication related.
- Postoperative constipation determined to be procedure and/or medication related.
- Postoperative pain that the Investigator considers common and within normal limits for the procedure and is well-managed with medication.
 - Pain that the investigator considers outside normal, or is not well-managed with medication, as well as pain that is severe (score 7 or higher on the VAS) and ongoing at the end of study will be reported as an AE in the eCRFs.

AEs will be collected and documented at baseline and 0 to 14 days follow-up.

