11.3. Adverse Event Recording

Assessment of the occurrence of an AE will be based on changes in the subject's physical examination, laboratory results and/or signs and symptoms. Adverse events will be monitored until a subject completes the study unless the Investigator determines the event is related to the device, in which case they will be monitored until resolution if possible. Medical care will be provided, as defined in the informed consent, for any AE related to study participation. Adverse events will be collected on an AE eCRF and applicable source documentation. To the extent possible, the event to be recorded and reported is the event diagnosis as opposed to event symptoms (e.g., fever, chills, nausea and vomiting in the presence of a clinically diagnosed infection is to be reported as infection only). For the purposes of this protocol, AEs will be collected and documented in a timely manner at baseline and 0 to 14 days follow-up.

The following should not be considered an AE:

- A condition requiring a preplanned procedure unless the condition worsened since screening
- A preexisting condition found as a result of screening, unless the condition has worsened since enrollment.

All responses to the above events that require treatment beyond the institution's standard procedures will be reported as AEs.

All AEs observed during the course of this study, regardless of severity or relationship to the device will be recorded on the appropriate eCRF except for what is noted in Section 11.1.1.

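### The CIP and SAP disagree on when adverse event collection starts, and the SAP's global and worst-severity AE figures can count subjects whose only event came before the device was used

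*Combined protocol and SAP*

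**What the plan says.** Several places include baseline in AE collection. CIP 11.1.1 says "AEs will be collected and documented at baseline and 0 to 14 days follow-up". CIP 11.1.2 to 11.1.5 say the same for SAEs, ADEs, SADEs and USADEs. CIP 11.3 repeats it: "AEs will be collected and documented in a timely manner at baseline and 0 to 14 days follow-up". SAP 7.10 uses the same window.

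Other places start later. CIP 9.7 says of the safety assessments: "Assessments will take place during the procedure through post-operative day 14 and will be recorded in the eCRF". In the study schematic (CIP 9.1.1, Table 1), the row "AE, SAE, ADE, USADE Assessment & Device Deficiencies" is blank under "Screening / Baseline Day -30 to 0" and is first marked in the Surgery (Day 0) column. The assessment list for the baseline visit in CIP 9.1.2 has no AE item, while the Day 0 list in CIP 9.1.3 has one.

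The interval before surgery varies by subject: "A screening/baseline visit will be performed within 30 days up to/on the day of the scheduled procedure".

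For the analysis, SAP 7.10 says "AEs will be presented globally and based on their occurrence periods: PRE-PROCEDURE, DURING PROCEDURE and POST-PROCEDURE" and "Safety analysis will be run on the whole ITT population and on the FAS". SAP 7.10.5 then summarises patients by worst severity and SAP 7.10.6 by worst relationship. Neither mentions onset relative to the procedure.

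**The concern.** This is a single-arm study, so background events cannot be offset against a control group. Readers are likely to take the overall AE percentage as a description of the device and the operation. If that percentage includes events with onset before the first use of the device, it describes something else. Because the documents disagree on the start of collection, it is also unclear which pre-procedure events are meant to be in the database at all.

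Two things are at stake: a clear definition of the headline safety percentage, and a collection window that can be stated without qualification in the report.

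**Working it through.** The plan states no AE rate and no computed figure on this point, so there is nothing to reproduce. The check compares the texts, follows the consequence through the SAP tables, and then bounds the size.

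**Step 1. Start of collection, side by side**

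| Place | Start of AE collection |
|---|---|
| CIP 11.1.1 to 11.1.5, 11.3 | Baseline, then days 0 to 14 |
| SAP 7.10 | Baseline, then days 0 to 14 |
| CIP 9.7 | During the procedure |
| CIP 9.1.1, Table 1, AE row | Surgery column (Day 0); Screening/Baseline blank |
| CIP 9.1.2, baseline list | No AE item |
| CIP 9.1.3, Day 0 list | AE/SAE assessment listed |

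All of these are current operative text, and they cannot all hold.

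**Step 2. Which subjects and events can enter**

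Safety is analysed on the ITT set and the FAS. Both contain only subjects who began the procedure (SAP 7.1.3), so events in screen failures stay out. Under CIP 11.3 a pre-existing condition found at screening is not an AE unless it has worsened since enrollment, and enrollment is the signing of consent (CIP 8.2). A new or worsened condition between consent and surgery, in a subject who is then operated on, therefore qualifies as an AE. SAP 7.10 gives it a named period and no rule that keeps it out of the global figure.

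**Step 3. What the by-period tables recover**

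Let B, D and P be the proportions of subjects with an event before, during and after the procedure, and G the global proportion. The quantity of interest is A, the proportion with any event at or after the start of the procedure.

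- A subject may appear in both D and P, so A lies between max(D, P) and D + P.
- A subject may appear in B and also later, so A lies between G − B and G.

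For illustration, D = 10% and P = 20% allow A anywhere from 20% to 10% + 20% = 30%. The period percentages bound A but do not give it.

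**Step 4. Size**

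Inputs: N = 48, the planned minimum (CIP 13.2), all taken to begin the procedure. The interval from screening to surgery, t, is 0 to 30 days (CIP 9.1.2). Two inputs are assumptions, because the documents give no rates: background AE incidence r of 2%, 5% or 10% per 30 days, and incidence p at or after the procedure of 10% to 40%. Earlier and later events are taken as independent, and collection as continuous from screening.

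Extra AE subjects = N × [1 − (1 − r)^(t/30)] × (1 − p)

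| t (days) | r | p | Extra subjects of 48 | Percentage points |
|---|---|---|---|---|
| 0 | any | any | 0 | 0 |
| 15 | 2% | 40% | 48 × 0.0101 × 0.60 = 0.29 | 0.6 |
| 15 | 5% | 40% | 48 × 0.0253 × 0.60 = 0.73 | 1.5 |
| 30 | 5% | 20% | 48 × 0.05 × 0.80 = 1.92 | 4.0 |
| 30 | 10% | 20% | 48 × 0.10 × 0.80 = 3.84 | 8.0 |
| 30 | 10% | 10% | 48 × 0.10 × 0.90 = 4.32 | 9.0 |

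The t = 0 row also assumes no event between arrival on Day 0 and the first incision.

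**The case against.** The strongest reply is that the SAP already separates the periods. It presents AEs before, during and after the procedure and adds a listing, so a reader can see which events preceded device use. The sentence stands at the head of SAP 7.10 and could be read as governing 7.10.5 and 7.10.6 as well. The table shells that might settle this are in a separate file. The study is descriptive, and the AE definition covers events whether or not they are related to the device. This reduces the harm considerably. What remains is that no planned summary gives the proportion with any event at or after the start of the procedure, and that 7.10.5 states no restriction.

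A reader might infer four stronger claims. The documents do not support them.

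- *Most of the AE window is pre-exposure time.* The share 30/(30 + 14) = 68%, or 30/(30 + 17) = 64% with the three extra days, is only a maximum. It needs screening on day −30 and continuous collection from then. The text may mean a single baseline visit followed by days 0 to 14, and same-day screening brings the share to about zero.
- *Following the schematic would remove the problem.* The schematic marks the whole of Day 0, and CIP 9.1.3 lists AE assessment alongside the pre-operative examination. Events on the day but before incision could still be captured.
- *Rates will not be comparable between sites.* Nothing shows that sites differ in screening interval or will follow different sections.
- *The relationship table is distorted.* SAP 7.10.6 lists the lack of a temporal relationship among the grounds for rating an event not related, so few pre-procedure events should be counted as related. A small residue is possible because the SAP codes an unlikely relationship as related.

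**Conclusion.** The point holds in a limited form. The start of AE collection is contradictory across the CIP and SAP. As written, the global AE presentation includes pre-procedure events and the worst-severity summary does not exclude them, so a subject with only a pre-exposure event can count as an AE subject. The by-period tables and the listing soften this but do not directly supply the proportion a reader would want.

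The size cannot be determined from the documents. It is zero with same-day screening and no pre-incision event. At the other end it reaches about four of 48 subjects, which needs a 30-day interval, continuous collection and an assumed 10% background rate. This is a cheap improvement to the reporting, and it does not threaten the study's conclusions.

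**What to change.** 1. Choose one start point for AE collection and state it identically in CIP 9.1.2, CIP 9.7, the AE row of the study schematic, CIP Section 11 and SAP 7.10. Say whether baseline means the visit only or the whole period from consent to surgery.
2. In SAP 7.10, define the headline AE incidence as the proportion of subjects with at least one event whose onset is at or after the start of the procedure. Apply the same restriction to the worst-severity table in 7.10.5 and, for consistency, to 7.10.6.
3. Report pre-procedure events in a separate count and listing, outside the headline percentage.

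The cost is a few lines of SAP wording, one onset filter in the AE tables and a short alignment of the CIP, which would follow the amendment route in CIP 15.6 if the sponsor classes it as an amendment. The one small downside is that pre-procedure events leave the headline percentage, but they remain reported.

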7.10.1 Serious Adverse Event

A serious adverse event (SAE) is any AE that has:

- led to death,
- led to serious deterioration in the health of the subject that either resulted in
 - a life-threatening illness or injury, or
 - a permanent impairment of a body structure or a body function, or
 - in-patient or prolonged hospitalization, or
 - medical or surgical intervention to prevent life threatening illness or injury or permanent impairment to a body structure or a body function, or
- led to fetal distress, fetal death, or a congenital abnormality or birth defect.

NOTE: Planned hospitalization for a pre-existing condition or a procedure required by the clinical investigational plan, without serious deterioration in health, is not considered an SAE.

SAEs will be collected and documented at baseline and 0 to 14 days follow-up.

7.10.2 Adverse Device Effect

An Adverse Device Effect (ADE) is an adverse event related to the use of an investigational medical device.

This definition includes adverse events resulting from insufficient or inadequate instructions for use, deployment, implantation, installation, or operation, or any malfunction of the investigational medical device.

This document is electronically controlled. Printed copies are considered uncontrolled.

Confidential

This definition includes any event resulting from use error or from intentional misuse of the investigational medical device.

Adverse Device Effects will be reported by the Investigator(s). If escalation is required, ADEs will be reviewed by medical affairs as part of Medtronic's Post-Market Vigilance program. Both confirmed and possible device related events will be included in the study report.

7.10.3 Serious Adverse Device Effect

A Serious Adverse Device Effect (SADE) is an adverse device effect that has resulted in any of the consequences characteristic of a serious adverse event.

SADEs will be collected and documented at baseline and 0 to 14 days follow-up.

7.10.4 Unanticipated Serious Adverse Device Effect

An Unanticipated Serious Adverse Device Effect (USADE) is a serious adverse device effect which by its nature, incidence, severity, or outcome has not been identified in the current version of the risk analysis report.

USADEs will be collected and documented at baseline and 0 to 14 days follow-up.

7.10.5 Adverse Event Severity Classification

Severity will be defined according to the following criteria:

Mild	Awareness of event, but easily tolerated
Moderate	Discomfort enough to cause some interference with activities of daily living (ADL)
Severe	Incapacitating, with an inability to perform ADL
Death	Death related to AE

An AE can be classified as severe and not deemed an SAE. Similarly, an SAE is not automatically severe in nature.

In this study, the incidence of patients by AEs category will be summarized by worst severity.

This document is electronically controlled. Printed copies are considered uncontrolled.

Confidential

7.10.6 Adverse Event Relationship Classification

Causality assessments define the relationship between the use of the medical device (including the medical-surgical procedure) and the occurrence of each adverse event, according to MEDDEV 2.7/3 Revision 3, May 2015 (Guidelines on Medical Devices, Clinical Investigations: Serious Adverse Event Reporting). During causality assessment activity, clinical judgment shall be used and the relevant documents, such as the Clinical Evaluation Report and the Risk Management Report shall be consulted, as all the foreseeable serious adverse events and the potential risks are listed and assessed there. The presence of confounding factors, such as concomitant medication/treatment, the natural history of the underlying disease, other concurrent illness or risk factors shall also be considered.

Each SAE will be classified according to five different levels of causality. The sponsor and the investigators will use the following definitions to assess the relationship of the serious adverse event to the investigational medical device or procedures:

Not related: relationship to the device or procedures can be excluded when:

1. the event is not a known side effect of the product category the device belongs to or of similar devices and procedures
2. the event has no temporal relationship with the use of the device or the procedures;
3. the serious event does not follow a known response pattern to the medical device (if the response pattern is previously known) and is biologically implausible;
4. the discontinuation of medical device application or the reduction of the level of activation/exposure - when clinically feasible - and reintroduction of its use (or increase of the level of activation/exposure), do not impact on the serious event;
5. the event involves a body-site or an organ not expected to be affected by the device or procedure;
6. the serious event can be attributed to another cause (e.g. an underlying or concurrent illness/ clinical condition, an effect of another device, drug, treatment or other risk factors);
7. the event does not depend on a false result given by the device used for diagnosis, when applicable;
8. harms to the subject are not clearly due to use error;
9. In order to establish the non-relatedness, not all the criteria listed above might be met at the same time, depending on the type of device/procedures and the serious event.

Unlikely: the relationship with the use of the device seems not relevant and/or the event can be reasonably explained by another cause, but additional information may be obtained.

Possible: the relationship with the use of the device is weak but cannot be ruled out completely. Alternative causes are also possible (e.g. an underlying or concurrent illness/ clinical condition or/and an effect of another device, drug or treatment). Cases where relatedness cannot be assessed or no information has been obtained should also be classified as possible.

Probable: the relationship with the use of the device seems relevant and/or the event cannot reasonably be explained by another cause, but additional information may be obtained.

Causal relationship: the serious event is associated with the device or with procedures beyond reasonable doubt when:

This document is electronically controlled. Printed copies are considered uncontrolled.

Confidential

1. the event is a known side effect of the product category the device belongs to or of similar devices and procedures;
2. the event has a temporal relationship with device use/application or procedures;
3. the event involves a body-site or organ that
 - a. the device or procedures are applied to;
 - b. the device or procedures have an effect on;
4. the serious event follows a known response pattern to the medical device (if the response pattern is previously known);
5. the discontinuation of medical device application (or reduction of the level of activation/exposure) and reintroduction of its use (or increase of the level of activation/exposure), impact on the serious event (when clinically feasible);
6. other possible causes (e.g. an underlying or concurrent illness/ clinical condition or/and an effect of another device, drug or treatment) have been adequately ruled out;
7. harm to the subject is due to error in use;
8. the event depends on a false result given by the device used for diagnosis, when applicable;
9. In order to establish the relatedness, not all the criteria listed above might be met at the same time, depending on the type of device/procedures and the serious event.

In this study, the incidence of patients with AEs related with study procedure or study device will be calculated. For each patients having at least one AE, their worst relationship will be identified. An AE will be considered as related when it is coded as:

Relationship	
Study CRF	Final code used (Not related/Related)
NOT RELATED	Not related
UNLIKELY	Related
POSSIBLE	Related
PROBABLE	Related
CAUSAL RELATIONSHIP	Related

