11.1.3. Adverse Device Effect (ADE)

In alignment with ISO 14155:2011 (Section 3.1), an Adverse Device Effect is an adverse event related to the use of an investigational medical device.

This definition includes adverse events resulting from insufficient or inadequate instructions for use, deployment, implantation, installation, or operation, or any malfunction of the investigational medical device.

This definition includes any event resulting from use error or from intentional misuse of the investigational medical device.

Adverse Device Effects will be reported by the Investigator(s). If escalation is required, ADEs will be reviewed by medical affairs as part of Medtronic's Post-Market Vigilance program. Both confirmed and possible device related events will be included in the study report.

Examples of adverse device effects include but are not limited to: unintended cutting, unintended electrical path, fire or explosion, or arching.

ADEs will be collected and documented at baseline and 0 to 14 days follow-up.

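### The SAP counts adverse events judged UNLIKELY as Related, so its related-AE incidence means 'relationship not excluded' and needs a possible-or-higher figure and the five levels beside it

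*Combined protocol and SAP*

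**What the plan says.** SAP 7.10.6 states that "the incidence of patients with AEs related with study procedure or study device will be calculated". Each patient with at least one AE is assigned his or her worst relationship level, and the level is converted to a two-way code. The conversion is introduced with "An AE will be considered as related when it is coded as" and set out in a table. Only NOT RELATED keeps the code Not related. POSSIBLE, PROBABLE and CAUSAL RELATIONSHIP become Related, and so does the level below them: "UNLIKELY Related". Both copies of the SAP text in the combined document carry the same table.

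Three definitions in the same section bear on that row:

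- The bottom level: "Not related: relationship to the device or procedures can be excluded when" listed criteria apply.
- The next level: "Unlikely: the relationship with the use of the device seems not relevant and/or the event can be reasonably explained by another cause".
- The default for cases that cannot be judged: "Cases where relatedness cannot be assessed or no information has been obtained should also be classified as possible".

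On reporting, CIP 11.1.3 says "Both confirmed and possible device related events will be included in the study report", and SAP 7.10.2 repeats the sentence. CIP 11.1.7 has the same five levels but no two-way recode. The SAP gives no reason for where it places the cut, and SAP 7.12 says that the analysis matches the CIP.

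**The concern.** A reader who sees an incidence of related AEs will normally take it to mean events that someone thought might be due to the device or the procedure. Under this table it also includes events that the raters leaned against attributing to either. Because the worst level per patient decides, a subject with a single AE rated UNLIKELY and nothing higher is counted as a related case.

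The study has one arm. No comparator is coded by the same rule, so the figure will be read on its own and perhaps set beside rates from other reports that may use a different cut. CIP 4.1 and 15.8 foresee publication. What is at stake is the meaning of a descriptive safety figure. No test, margin or stopping rule depends on it.

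**Working it through.** The plan states no expected related-AE rate, so there is no figure to reproduce. The check has two parts.

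**Part 1: the row against the scale (SAP 7.10.6).**

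1. UNLIKELY and PROBABLE are worded as mirror images. In the first, the link seems not to matter or another cause reasonably explains the event. In the second, the link seems to matter or no other cause reasonably explains it. The table gives both the same final code.
2. Doubt already has its own level. POSSIBLE covers links that cannot be ruled out and takes unassessable cases by default. CIP 11.1.7 also sends remaining sponsor uncertainty there. UNLIKELY is therefore a judgement leaning against relatedness.
3. The boundary between UNLIKELY and NOT RELATED is thin. Criterion 6 for NOT RELATED is that the event can be put down to another cause, and criterion 9 says that not all criteria need be met. That is close to the definition of UNLIKELY, yet the two levels receive opposite final codes. The Related count thus depends on a label choice that raters may find hard to make consistently.
4. Against this, NOT RELATED requires that the relationship can be excluded, and UNLIKELY does not reach that standard. The table is coherent as a rule that anything not excluded counts as Related.

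**Part 2: the effect on the incidence.**

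Inputs:

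- N: at least 48 subjects, up to 3 sites, at most 24 per site (SAP section 5), so at most 3 × 24 = 72. The safety analysis uses the ITT set and the FAS (SAP 7.10), so the actual denominator may differ from the number enrolled.
- r: subjects whose worst level is POSSIBLE or higher. Not given; assumed.
- u: subjects whose worst level is UNLIKELY. Not given; assumed.

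Formulas: SAP grouping = (r + u)/N; possible-or-higher = r/N; difference = u/N, which is never negative.

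Per subject with worst level UNLIKELY: 1/48 = 2.08 percentage points; 1/72 = 1.39 percentage points.

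| N | r (assumed) | u (assumed) | SAP grouping | Possible or higher | Difference (points) |
|---|---|---|---|---|---|
| 48 | 2 | 0 | 2/48 = 4.2% | 2/48 = 4.2% | 0 |
| 48 | 2 | 3 | 5/48 = 10.4% | 2/48 = 4.2% | 6.2 |
| 48 | 2 | 5 | 7/48 = 14.6% | 2/48 = 4.2% | 10.4 |
| 48 | 10 | 10 | 20/48 = 41.7% | 10/48 = 20.8% | 20.8 |
| 72 | 2 | 3 | 5/72 = 6.9% | 2/72 = 2.8% | 4.2 |
| 72 | 2 | 5 | 7/72 = 9.7% | 2/72 = 2.8% | 6.9 |

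For scale, the exact (Clopper-Pearson) 95% intervals are 3.5 to 22.7% for 5/48 and 0.5 to 14.3% for 2/48. The direction is certain. The size cannot be found from the documents.

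**The case against.** The best defence is that the row is a deliberate safety convention. NOT RELATED is defined by exclusion, and the SAP nowhere says that UNLIKELY means Not related. A sponsor that takes part in judging causality does well not to choose the cut that lowers its own related-AE count. The rule is written down in advance, and (r + u)/N is a valid upper bound on the possible-or-higher rate. All of that stands. A reader might infer that the SAP contradicts its own definition, but the documents do not support so strong a reading.

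A reader might also infer that the rule breaches the CIP's threshold for device-related events. It does not. The sentence in CIP 11.1.3 says which events must appear in the report, and including more does not violate it. It is not a rule for collapsing five levels into two: its word for the definite cases is not a level on the scale, and PROBABLE is not named. The affected statistic also covers the procedure as well as the device, so it is not a rate of adverse device effects. The sentence shows a difference in emphasis only.

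On size, CIP 11.1.1 removes common expected events, such as transient nausea and well-managed pain, from reportable AEs. Large values of u, such as the 10 in the table, may therefore be too high. The planned AE listing and the worst-relationship derivation mean that little information is lost.

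What the defence does not answer is the label. Precaution is already built into POSSIBLE, no reason is given for going one level lower, and the word Related does not tell the reader that UNLIKELY is inside it.

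**Conclusion.** The point holds as one of labelling and presentation. The Related incidence in SAP 7.10.6 is really an incidence of relationship not excluded, and the plan does not call for the possible-or-higher figure that most readers would expect.

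It would go too far to say that the plan overstates the related-AE rate. That depends on taking possible-or-higher as the reference and on u being above zero. If no subject's worst level is UNLIKELY, the two figures agree. If some are, the gap is u/N. Every value of r and u used here is an assumption. The study is descriptive, its primary endpoint is VAS pain, and nothing in its conclusions turns mechanically on this rate. The reason to act is that a single-arm safety figure is read alone, and the clarification is cheap.

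**What to change.** In SAP 7.10.6:

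1. Report the incidence of patients with related AEs with Related defined as POSSIBLE, PROBABLE or CAUSAL RELATIONSHIP.
2. Keep the present grouping as a second row, labelled 'relationship not excluded (includes UNLIKELY)', and give the reason for showing it in one sentence.
3. Tabulate subjects by worst relationship at all five levels, separately for device and procedure where the CRF allows. CIP 11.1.7 already asks for that distinction for serious events.

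The cost is one extra row and a small table, all from data already collected. The drawback is that the possible-or-higher figure is less conservative than the current one. Showing both rows together offsets this.
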